**STATEMENT OF COMPLIANCE**

This document is a protocol for a clinical research study. The study will be conducted in compliance with all stipulations of this protocol, the conditions of ethics committee approval, the NHMRC National Statement on Ethical Conduct in Human Research (2007) and the Note for Guidance on Good Clinical Practice (CPMP/ICH-135/95).

## TABLE OF CONTENTS

STATEMENT OF COMPLIANCE .....	1
1. STUDY MANAGEMENT .....	6
2. INTRODUCTION AND BACKGROUND .....	11
3. STUDY OBJECTIVES .....	13
4. STUDY DESIGN.....	14
5. PARTICIPANT ENROLMENT AND RANDOMISATION .....	16
6. STUDY PROCEDURES SCHEDULE .....	19
7. STATISTICAL METHODS.....	30
8. ADVERSE EVENT REPORTING .....	31
9. DATA MANAGEMENT .....	32
10. ADMINISTRATIVE ASPECTS.....	34
11. USE OF DATA AND PUBLICATIONS POLICY .....	34
12. REFERENCES .....	35

PROTOCOL SYNOPSIS

Title	Active Women over 50: an effectiveness implementation randomised controlled trial
Objectives	
Primary: To evaluate the effectiveness of the Active Women over 50 program on daily steps at 6 months compared with waitlist control among women aged 50+ years.
 
Secondary: (1) To evaluate the effectiveness of the Active Women over 50 program on physical activity participation, falls, mental wellbeing, physical function, quality of life, sleep, bodily pain, menopause symptoms, balance, fear of falling, action planning and coping planning at 6 months after randomisation; (2) to evaluate the effectiveness of the Active Women over 50 program on goal attainment at 6 months after randomisation; (3) to evaluate the proportion of participants who i) achieve light physical activity and lower limit MVPA/week; ii) increase their daily steps by 2000+ from baseline to 6 months after randomisation; (4) to explore the experiences of participants in the Active Women over 50 program and to investigate contextual factors that affect the program uptake and maintenance; (5) to evaluate the cost-effectiveness, implementation potential, and determinants to guide scale-up; (6) to test secondary implementation outcomes (reach, fidelity and adoption, dose, sustainability); (7) To evaluate the number of daily steps for intervention participants 6 months after the program has ended, at 12 months after randomisation; (8) to evaluate the effect of the Active Women over 50 program on physical activity, falls, mental wellbeing, physical function, quality of life, sleep, bodily pain, menopause symptoms, balance, fear of falling, action planning, and coping planning for intervention participants 6 months after the program has ended, at 12 months after randomisation; (9) to evaluate the proportion of intervention participants who i) achieve light physical activity and lower limit MVPA/week, ii) increase their daily steps by 2000+ from 6 to 12 months after randomisation.

Study Design	We will conduct a two-arm parallel pragmatic hybrid type I effectiveness-implementation randomised controlled trial.
Planned Sample Size	1000 women aged 50 years and over.
Selection Criteria	Inclusion criteria: Eligible participants will be women aged 50 years and over, who are community-dwelling residents in NSW, not currently meeting the physical activity guidelines, have access to an internet connected device and who want to receive support to be more active.

	
Exclusion criteria: People will be excluded if they have limited English language skills, have a medical condition that precludes participation in regular physical activity, have cognitive impairment (Memory Impairment Screen [MIS]<5), have a progressive neurological disease, or are unable to leave the house independently or walk 10 metres unassisted.


Study Procedures
	
Trial participants will be recruited via advertisements in community newsletters, websites and mainstream and social media, and through research volunteer registries, community organisations and health promotion services targeting women. After telephone screening for eligibility and upon giving informed consent, participants will complete a baseline survey including questions about general health and surveys related to secondary outcomes. They will wear an accelerometer device (ActiGraph) over 7 days to determine their baseline physical activity including average daily step count. They will then be randomly allocated to either the intervention group, (n=500), or a waitlist control group, (n=500). Participants will complete a similar survey at 6 months post-randomisation and will wear the accelerometer again at 6 months post-randomisation for 7 days to determine end of program daily step count and physical activity. . Intervention participants will be invited to extend their participation in the study for a further 6 months to complete a similar survey and wear the accelerometer again at 12-months post-randomisation to determine daily step count and physical activity maintenance. Completion of this extra follow-up will be optional.
 
The intervention group will receive access to Active Women over 50 program, which includes telephone health coaching, email or SMS motivational messages incorporating several behaviour change techniques (BCTs), a program-specific website and a private Facebook page to support their physical activity. The control group will be waitlisted to receive the Active Women over 50 program after completing all 6-month follow-up measures.

Statistical Procedures Analysis Plan Sample Size
	
Analysis Plan
 
The primary outcome will be analysed using generalised linear regression to assess the effect of group allocation at 6 and 12 months, with its corresponding baseline score as a covariate. Continuous secondary outcomes will be analysed using linear regression, adjusting for the corresponding baseline measure of the outcome variable as appropriate. We will use log-binomial regression to determine the between-group difference in the proportion of people increasing daily steps by 2000+. Fall rates will be analysed using negative binomial regression models to estimate the difference in rates between groups after 6 months. There

	
will also be pre-defined subgroup analyses included by age, number of medical conditions and baseline fall history.
 
Sample size: A sample size of 1000 people will provide 90% power to detect a between-group difference of 1000 steps/day (SD 4200), assuming 25% dropouts, alpha 5%. The sample size calculation was undertaken using the sampsi command in Stata.

Duration of the study	
We aim to recruit all participants between December 2023 and December 2025 and complete follow-up by June 2026. Data analysis and report writing will be completed by December 2026.

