### **3.2 Secondary Objectives**

Secondary aims are (1) to evaluate the effectiveness of the Active Women over 50 program on physical activity, falls, mental wellbeing, physical function, quality of life, sleep, bodily pain, menopause symptoms, balance, fear of falling, action planning, and coping planning at 6 months after randomisation; (2) to evaluate the effectiveness of the Active Women over 50 program on goal attainment at 6 months after randomisation; (3) to evaluate the proportion of participants who i) achieve light physical activity and lower limit MVPA/week, ii) increase their daily steps by 2000+ from baseline to 6 months after randomisation; (4) to explore the experiences of participants of the Active Women over 50 program and to investigate contextual factors that affect the program uptake and maintenance; (5) to assess the cost-effectiveness, implementation potential and determinants to guide scale-up from the perspective of the healthcare and community funder; (6) to test secondary implementation outcomes (reach, fidelity and adoption, dose, sustainability); (7) To evaluate the number of daily steps for intervention participants 6 months after the program has ended, at 12 months after randomisation; (8) to evaluate the effect of the Active Women over 50 program on physical activity, falls, mental wellbeing, physical function, quality of life, sleep, bodily pain, menopause symptoms, balance, fear of falling, action planning, and coping planning for intervention participants 6 months after the program has ended, at 12 months after randomisation; (9) to evaluate the proportion of intervention participants who i) achieve light physical activity and lower limit MVPA/week, ii) increase their daily steps by 2000+ from 6 to 12 months after randomisation.

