**Table 3 Schedule of assessments**

--	--

TIME POINT	-t 1	0	t 1	t 2	t 3	Monthly
ENROLMENT:						
Eligibility screen	✓					
Informed consent	✓					
Baseline surveys, Device measured activity Actigraph	✓					
Randomisation / Allocation		✓				
INTERVENTIONS:						
Active Women over 50 program		✓				
Waiting list control				✓		
OUTCOMES						
Number of falls measured with monthly calendars for 6 months						✓
Device-measured outcomes using Actigraph	✓		✓		✓	
Individualised goal attainment	✓		✓			
Self-reported secondary outcome measures	✓		✓		✓	

-t1: baseline, prior randomisation; 0: after randomisation, t1: 6-month follow-up; t2: after 6-month follow-up completed; t3: 12-month follow-up for intervention group participants

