### **7.2 Statistical Analysis**

Analyses will be guided by a rigorous statistical analysis plan developed a priori as we have done previously and use an intention-to-treat approach. The primary outcome will be analysed using generalised linear regression to assess the effect of group allocation, with its corresponding baseline score as a covariate. Continuous secondary outcomes will be analysed using linear regression adjusting for the corresponding baseline measure of the outcome variable as appropriate. We will use log-binomial regression to determine the between-group difference in the proportion of people increasing daily steps by 2000+. Fall rates will be analysed using negative binomial regression models to estimate the difference in rates between groups after 6 and 12 months with exploratory analyses adjusting for amount of physical activity. There will also be pre-defined subgroup analyses included by age, rurality/remoteness of residence, number of medical conditions and baseline fall history. Analyses will be conducted using Stata 14 software.

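### The 12-month between-group analyses of steps (synopsis) and fall rates (section 7.2) cannot be estimated, because no controls are scheduled for measurement after month 6

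*Protocol*

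**What the plan says.** **Analysis text.** The synopsis (Statistical Procedures) analyses the primary outcome by generalised linear regression "to assess the effect of group allocation at 6 and 12 months, with its corresponding baseline score as a covariate". For falls, the same synopsis plans only to "estimate the difference in rates between groups after 6 months". Section 7.2 reverses the pattern. Its steps sentence names no time point: "The primary outcome will be analysed using generalised linear regression to assess the effect of group allocation, with its corresponding baseline score as a covariate". Its falls sentence uses "negative binomial regression models to estimate the difference in rates between groups after 6 and 12 months".

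**Design text.** The synopsis (Study Procedures) states: "The control group will be waitlisted to receive the Active Women over 50 program after completing all 6-month follow-up measures". Table 3 places the waitlist group's program at t2, after the 6-month follow-up, and defines t3, the 12-month visit, as a visit for intervention participants. Sections 4.1, 5.4, 6.2.2, 6.6 and 9.1 agree that only intervention participants go on to month 12, and sections 5.4, 6.6 and 9.1 add that this needs further consent. The synopsis calls the extension optional.

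**Outcomes.** Section 6.2 fixes the primary outcome at 6 months. Table 2 lists 12-month steps as secondary. Objectives 7 to 9 in section 3.2 restrict the 12-month questions to intervention participants; objective 8 is "to evaluate the effect of the Active Women over 50 program on physical activity, falls, mental wellbeing" and further outcomes in that arm. Sections 3.2 and 6.2 include falls among the 12-month outcomes. Table 2 names the monthly falls calendar as the falls measure, and Table 3 schedules "monthly calendars for 6 months".

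**The concern.** A group coefficient at month 12 needs outcome data from both groups at month 12. The protocol collects them in one. An analyst following the text would have to omit a prespecified analysis or improvise a comparator, and the steps version of the problem sits in the sentence that defines the primary analysis. The disagreement between the synopsis and section 7.2 also means that neither can be used to settle what was meant by the other.

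The wording of conclusions is affected too. Objective 8 speaks of an effect at 12 months, and research question 6 (section 2.2) of an impact. Data from one arm, in participants who chose to continue, can show change or maintenance, but cannot separate the program from time, season or selection.

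**Working it through.** **1. The plan's own figure, to confirm what is not affected.** Section 7.1 gives a difference of 1000 steps/day, SD 4200, alpha 5% (two-sided assumed; sidedness is not stated), power 90%, 25% dropout and 500 per group.

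- Evaluable per arm: n = 2 × (1.960 + 1.282)² × 4200² / 1000² = 2 × 10.51 × 17.64 ≈ 371.
- Inflated for dropout: 371 / (1 − 0.25) = 494.7, so 495 per arm, or 990 in total. The stated 1000 is reproduced within rounding.
- Power with 500 × 0.75 = 375 evaluable per arm: the standard error is 4200 × √(2/375) ≈ 306.7; 1000/306.7 − 1.960 ≈ 1.30, which gives 90.3%.

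This calculation concerns month 6 only and stands as written.

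**2. Planned between-group analyses against available data.**

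| Outcome and time | Synopsis | Section 7.2 | Controls scheduled for measurement |
|---|---|---|---|
| Steps, 6 months | yes | time point not named | yes |
| Steps, 12 months | yes | not stated | 0 |
| Fall rate, 6 months | yes | yes | yes |
| Fall rate, 12 months | not stated | yes | 0 |

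Table 1 (section 4.2) points the same way: its 12-month row covers intervention participants only, at 100 + 200 + 200 = 500. That is the whole arm, so it is a ceiling for an optional visit. There is no 12-month row for controls.

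**3. Consequence for the models.** Among observations at month 12 the group indicator takes a single value. It is then collinear with the intercept, so the steps model has no estimable group coefficient. The fall rate ratio for 12 months likewise has no control data beyond month 6. No sample size changes this.

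**4. If controls were measured at month 12 after all.** They would already have been offered the program. The contrast would be immediate against delayed program, which is a different question from program against no program.

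**5. Falls in months 7 to 12, intervention arm.** Falls are listed as a 12-month outcome (sections 3.2 and 6.2). The named instrument is the monthly calendar (Table 2), scheduled for 6 months (Table 3). Section 6.2.2 says that 12-month outcomes are assessed by survey and accelerometer, and Table 3 ticks self-reported secondary outcomes at t3, but no section says that the survey carries a falls question. The source of 12-month falls is therefore unclear.

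**The case against.** The strongest reply is that this is uneven drafting and not a settled plan. Each analysis text lacks the slip found in the other, objectives 7 to 9 already confine month 12 to intervention participants, and the synopsis describes the extension as a look at maintenance. Because the model cannot be fitted as scheduled, it cannot itself produce a misleading randomised estimate. All of this is fair. It shows that the analysis sentences are what must change, but it does not make them correct: both are stated as between-group analyses, and both are impossible on the schedule.

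Some stronger readings are tempting and should not be drawn.

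- *Month 12 has become a co-primary time point.* The primary objective (section 3.1) and the outcome definition (section 6.2) both fix month 6, and Table 2 makes 12-month steps secondary. One phrase in the synopsis does not override these.
- *Twelve-month falls have no data source at all.* The self-report survey at t3 may supply them, and the monthly health diaries in section 6.6 ask about exercise-related falls with no 6-month limit stated there. What is supportable is that the named calendar stops at 6 months and that no other source is specified for the fall rate.
- *The 12-month sample is capped at 375.* The 25% dropout is a planning assumption. Section 6.5.3 states 20%, which would give 500 × 0.80 = 400, and Table 1 plans 500. The documents give no opt-in rate. None of this matters to the point, which rests on the absence of controls.
- *The trial intends to set 12-month intervention data against 6-month control data.* Nothing in the protocol proposes it. It is only a risk if the text is left for an analyst to interpret.

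**Conclusion.** The point holds, confined to month 12. Two between-group analyses, steps in the synopsis and fall rates in section 7.2, are specified at a time when 0 of the 500 controls are scheduled for measurement and when controls have already been offered the program. The synopsis and section 7.2 also contradict each other on which outcome carries the 12-month comparison. The 6-month primary comparison and its power (90.3% with 375 evaluable per arm) are unaffected. The conclusion rests only on the follow-up schedule and the crossover as the protocol describes them; it needs no assumption about dropout or opt-in. Separately, ascertainment of falls between months 6 and 12 is not reconciled between the outcome lists and Tables 2 and 3.

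**What to change.** 1. In the synopsis, remove the reference to 12 months from the primary-outcome sentence. In section 7.2, remove it from the falls sentence and name month 6 in the steps sentence, so that the two texts agree and month 6 is the only randomised contrast.
2. State that 12-month data are reported as uncontrolled within-arm change (maintenance) in intervention participants who opted in, with confidence intervals and no between-group test. The model itself can be left to the statistical analysis plan.
3. Word the conclusions for objective 8 and research question 6 as change or maintenance, not as an effect of the program.
4. Either drop falls from the 12-month outcomes or state that they come from the 12-month survey. In the second case, note that a survey report is a different instrument from the monthly calendar, so the result is not directly comparable with the 6-month rate.

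The cost is a wording amendment, submitted to the ethics committee as section 10.2 requires. It needs no extra participants and costs no power. The price is that the 12-month results support only a descriptive statement about maintenance, which is all that the present design can support.

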### **1.5 Internal Trial Committees**

The Steering Committee is responsible for study conception, design, protocol refinement, fund procurement and providing the scientific direction of the study. The Steering Committee will ensure that the research is carried out in accordance with national guidelines on the conduct of research in humans.

### **1.6 Sponsor**

The University of Sydney.

### **1.7 Funding and resources**

The study is being funded through the Medical Research Future Fund Effective Treatments and Therapies grant (MRF2023710) and Medical Research Future Fund Dementia Ageing and Aged Care Mission grant (MRF2024387).

## **2. INTRODUCTION AND BACKGROUND**

### **2.1 Background Information**

Physical inactivity is a significant public health concern in Australia. Australian national guidelines recommend that adults should undertake at least 150 minutes of moderate to vigorous intensity physical activity per week plus muscle strengthening activities twice a week. Despite the clear physical and mental health benefits of physical activity, as few as 13% of Australian women aged 45-64 years meet both the physical activity and strength guidelines. Alarming, the annual cost of physical inactivity has been estimated to be a staggering \$805 million in Australia, including direct costs (healthcare expenditure) and indirect costs (lost productivity).

Middle age is a crucial time for physical activity. Middle-aged and older adults are a priority group for targeted physical activity programs, since physical capacity starts to decline at around age 50, and older people are generally the most inactive. Regular physical activity in younger years delays age-related decline in physical capacity and disability in women aged 70+ by up to 15 years. Mid-life physical activity is particularly relevant because it is also associated with a higher likelihood of being physically active in older age and reduces the risk of falls, several chronic conditions and cancers, and increases recovery after an acute event. Moreover, physical activity commenced in middle-age years (40–65 years) can reduce the all-cause risk for mortality irrespective of past physical activity levels or the intensity of physical activity.

Women in middle age have unique barriers to being active, such as multiple caring responsibilities and the onset of chronic conditions, yet very few evidence-based, low-cost, scalable approaches to physical activity aim to reach a large proportion of them. For example, in Australia, women comprise 47% of the Australian labour force and compared to men, they juggle employment with higher primary carer responsibilities: 69% of carers aged 45–64 years are women.

Moreover, 62% of women in this age group live with at least one chronic condition. There are personal, cultural and structural barriers to physical activity for women in this age group. The onset of menopause can bring physical changes (such as hot flushes, weight gain and fatigue) that are barriers to being active. Women may be aware of the benefits physical activity can have on these symptoms and bodily changes but may perceive negative attitudes while exercising in public. Women in regional and remote areas may face additional barriers due to geography and access to physical activity opportunities and services. The competing demands and specific barriers to exercise that middle-aged women experience necessitate targeted support to encourage the adoption and maintenance of regular physical activity for healthy ageing.

Our previous systematic review demonstrates the beneficial effects of health coaching. Health coaching had a small, statistically significant effect on physical activity. However, there was no evidence of an effect of health coaching on mobility, quality of life, and mood, suggesting that, to address all project objectives, health coaching should be combined with other approaches, such as online information provision, or social support. Health promotion interventions that aim to change lifestyle behaviours, which are delivered by digital technologies, offer an efficient, effective, and scalable solution for preventing noncommunicable diseases and addressing physical inactivity. Community members are now generally savvy digital service users thanks to COVID-19. The virtual, technology-driven design of this research supports rapid, implementation nationwide, including rural/regional Australia, and helps address the time challenges experienced by many women due to competing pressures.

We developed and pilot-tested the Active Women over 50 program among 62 women aged 50+ years. Our pilot process and impact evaluation results demonstrated high acceptability and uptake. The intervention participants increased daily steps from baseline by 2000+ steps (OR 6.31, 95%CI: 1.22 to 32.70), and increased their overall physical activity levels (light, moderate, and vigorous intensities) more than controls. The high uptake, engagement, positive recommendation (87% would

recommend to others), and promising impact on physical activity provided evidence and justification to conduct a larger trial.

